Nature and extent of the burden and risks associated with participation, benefit and group relatedness: Couples with infertility will receive standard fertility treatment, i.e. EM or ART. The risks and burden of participating in the trial are small. After a complete diagnostic work-up for infertility, the males will be randomised for use of either Impryl® or placebo. Impryl® is a food supplement already free available throughout Europe, online in the

Netherlands. Males need to take study medication (one tablet each day) for a maximum of 6 months in total. For this study, we want to measure improvement of semen parameters after at least 3 months use of study medication. Performing a pre-wash TMS is standard procedure at most sites when semen is used for IUI or IVF/ICSI. However, in couples with EM performing a TMS after 3 months is not standard care. We decided not to perform a semen analysis in the EM group due to the fact that improvement in fertility treatment from expectative management is not possible. Participants are required to collect study medication directly at their local hospital or at Radboudumc. At the start of taking study medication the couple is asked to fill in a questionnaire about their baseline characteristics. To assess lifestyle changes during intervention and amount of used study medication, every male will be asked each month (6 times in total) to fill in an online questionnaire, these monthly questionnaires stop when a pregnancy has been reached. Every couple will receive a final questionnaire, 15 months after inclusion, about the outcome of fertility treatment and occurrence of pregnancy. If a woman is pregnant, standard care is an ultrasound around 10-12 weeks to estimate the due date. To limit the amount of extra site visits to zero, we decided that this 'due date' ultrasound at 10-12 weeks of pregnancy is enough for determining the primary outcome. The ultrasound can be made in the midwife practice. Information about the outcome of this ultrasound is reported in the 15-months questionnaire. In conclusion, the burden and risks associated with participation in this trial can be considered negligible.

INTRODUCTION AND RATIONALE

[figure not shown]

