Number of pregnancies conceived in the optimal intervention time window, i.e. between start of month 4 till the end of month 6. Overall pregnancy rate. Time to pregnancy defined as both the time between a) randomization and reaching ongoing pregnancy, and as b) start of fertility treatment during the study (EM, IUI, IVF/ICSI) and reaching ongoing pregnancy. Change in semen parameters leading to different fertility treatment categorisation (for more details see page 26) between baseline and 3 months intervention, based on pre-wash total motile sperm count (TMSC) from the subpopulation from Radboudumc and sites that deliver a pre-wash TMSC before IUI/IVF/ICSI. Improvement between Impryl® and control group in fertilization rate and embryo-utilization rate in IVF/ICSI group. Fertilization rate is defined as the percentage of oocytes with 0 PN or ≥ 2 PN after insemination (IVF) or injection (ICSI). Abnormal fertilization such as 3PN will be recorded, in case this percentage differs or increases in the study group. The embryo-utilization rate (EUR) is defined as the number of high quality embryos obtained, embryo's used at transfer plus the number of embryos frozen, divided by the number of zygotes obtained in a cycle. Due to the differences in embryo evaluation and embryo selection criteria for cryopreservation, we decided to measure the relative increase in fertilization and utilization rate observed for each clinic.. Number of miscarriages defined as a non-vital intra-uterine pregnancy before 16 weeks of gestation. Live birth rate defined as beyond 24 weeks of gestation, the birth of a living child. Live births (beyond 24 weeks, defined as the birth of a living child) will be reported within follow-up time of 15 months. Furthermore the following adverse events will be reported: gastro-intestinal problems such as reflux, obstipation, diarrhea, nausea or vomiting, furthermore loss of appetite, headache, dizziness, pruritus or skin rash.

STUDY DESIGN

A multicentre randomised, double blind placebo controlled, clinical trial for Impryl® administration will be performed in the Department of Gynaecology and/or Reproductive Medicine in both academic and non-academic hospitals in The Netherlands.

The 16 centers participating in the study:

| Hospital | Principal investigator |
|---|--------------------------------|
| Radboudumc, Nijmegen | [name] |
| Slingeland Ziekenhuis, Doetinchem | [name] |

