1.2 Inclusion criteria

In order to be eligible to participate in this study, a subject must meet all of the following criteria:

- Either: couples with failure to conceive for at least 12 months and starting with EM **or** couples starting with 1st/ 2nd/3rd cycle of IUI (with/without ovarian stimulation) **or** 1st/ 2nd/3rd cycle of IVF/ICSI
- Male with age 18-50 years
- Female partner with age 18-43 years
- Willing and able to give informed consent

Exclusion criteria

A potential subject who meets any of the following criteria will be excluded from participation in this study:

- Planned or performed diagnostic testicular biopsy (TESE) or percutaneous epididymal sperm aspiration (PESA)
- Use of donor-, cryopreserved- or electro-ejaculated semen
- Ovulation induction (OI) without IUI
- IVF for an absolute tubal factor
- Embryo-transfers after cryopreservation
- Embryo-transfer after pre-implantation genetic diagnosis
- Known endocrine abnormalities related to infertility, or use of fertility enhancing drugs
- Known genetic abnormalities related to infertility
- Known urological abnormality such as a varicocele or bilateral cryptorchism
- Use of other vitamin supplements

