1.3 Sample size calculation

The overall success rate (number of ongoing pregnancies, not specified per cycle number) in IVF and ICSI in the Netherlands was respectively 19.8% and 21.5% per cycle in 2015.(23) The cumulative number of ongoing pregnancies in IUI is estimated to be around 5 to 13% per cycle, around 18% after three cycles and 20-30% after six cycles. (24-26) Based on our Radboudumc data, the ongoing pregnancy rate in EM is estimated around 20% after 6 months.

A Cochrane review ‘antioxidants for male subfertility’ estimated the increase in clinical pregnancy rates after use of antioxidants with an Odds Ratio (OR) of 3.43 (95% CI 1.92 to 6.11, $P < 0.0001$, 7 RCTs, 522 men, $I^2 = 0\%$, low quality evidence). (27) However, this concerns low quality evidence, and the included population in this Cochrane review was couples with male factor subfertility, whereas in our study we also include couples with unexplained infertility. Therefore, we assumed a more conservative OR of 1.5. Assuming a 20% ongoing pregnancy rate in the placebo group, this reflects in an expected pregnancy rate of 27.3% in the Impryl® group

The study is designed as a superiority study. Based on the above mentioned data, we expect a 7.3% increase in ongoing pregnancy number when men are treated with Impryl® compared to placebo. However, after randomization patients can directly start with both intervention and achieving a pregnancy, either spontaneously or with fertility treatment. In these first months the effect of the intervention is expected to be suboptimal due to the duration of the spermatogenesis (72 days before whole renewal). Therefore we adjusted the expected increase of 7.3% to a more realistic effect of 6.5%. We assume an equal increase in all fertility groups (meaning EM, IUI and IVF/ICSI) from 20% to 26.5%.

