5.1.2 Secondary study parameters/endpoints

Number of pregnancies conceived in the optimal intervention time window, i.e. between start of month 4 till the end of month 6.

Overall number of pregnancies meaning the cumulative pregnancy number up to 9 months after start of intervention

Time to pregnancy defined as

- a) the time between start randomization and reaching ongoing pregnancy (confirmed by ultrasound)
- b) the time between start of fertility treatment during the study (EM, IUI, IVF/ICSI) and reaching ongoing pregnancy

Change in semen parameters in IUI/IVF/ICSI group based on pre-wash total motile sperm count (TMSC), leading to different fertility treatment categorisation (EM, IUI, IVF, ICSI), from a subpopulation of patients: Radboudumc patients and patients from other sites having pre-wash TMSC as standard procedure when semen is used for IUI or IVF/ICSI.

Improvement between Impryl® and control group in fertilization rate and embryo-utilization rate in IVF/ICSI group. Fertilization rate is defined as the percentage of oocytes with 0 PN or ≥ 2 PN after insemination (IVF) or injection (ICSI). Abnormal fertilization such as 3PN will be recorded, in case this percentage differs or increases in the study group. The embryo-utilization rate (EUR) is defined as the number of high quality embryos obtained, embryo's used at transfer plus the number of embryos frozen, divided by the number of zygotes obtained in a cycle. Due to the differences in embryo evaluation and embryo selection criteria for cryopreservation, we decided to measure the relative increase in fertilization and utilization rate observed for each clinic.

Number of miscarriages (defined as non-vital intra-uterine pregnancy before 16 weeks of gestation)

Live birth rate (beyond 24 weeks, defined as the birth of a living child) within study-period of 15 months

Adverse effects

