Semen analysis will be performed two times: once during diagnostic work-up (standard care, analysis according to WHO criteria(28) and once more after approximately 3 months of using study medication (ie. after three months of IUI treatment or IVF/ICSI). At several sites, a pre-wash TMSC is standard care when performing an insemination (IUI group) and will be performed on the semen produced for IVF/ICSI as part of routine measurement before procedure. Because semen analysis performed at the time of treatment cannot be fully performed according to the WHO criteria, we will categorize the TMSC quality according to the allocated treatment category. This means, that the TMSC (evaluated at the start of treatment and after 3 months) will be analyzed according to changes in allocated treatment category based on the NVOG guideline(29). The criteria for treatment are given in the table below. A change in treatment category means an improvement in sperm quality that would allow a lower treatment category (e.g, from ICSI to IVF)

| TMSC outcome ($\times 10^6$) | WHO Diagnostic category | NVOG Treatment category |
|--------------------------------|-------------------------|---|
| > 10 | Normospermia | EM |
| 3 -10 | Mild OAT | IUI |
| 1-3 | OAT | IVF/ICSI (if after wash VCM is <0,5) |
| <1 | Extreme OAT/Azoospermia | ICSI |

OAT = oligo-astheno-teratozoospermia.

* Or IVF depending on the prediction model of Hunault and other clinical characteristics

We decided not to perform a semen analysis in the EM group due to the fact that they already have normal semen parameters at intake and the burden of an extra visit is high.

Fertilization and embryo-utilization rate

In IVF/ICSI patients fertilization rate and embryo-utilization rate are standard reported by every IVF-laboratory. Fertilization rate is the percentage of oocytes with ≥ 2 PN after insemination (IVF) or injection (ICSI). The embryo-utilization rate (EUR) is defined as the number of high quality embryos obtained, embryo's used at transfer plus the number of embryos frozen, divided by the number of zygotes obtained in a cycle. Due to the differences in embryo evaluation and embryo selection criteria for cryopreservation, we decided to measure the relative increase in fertilization and utilization rate observed for each clinic.

Transvaginal ultrasonography

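### Section 5.3 does not secure three months of tablet use before the follow-up TMSC, and the fertilization and embryo-utilization rates have no exposure condition

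*Combined protocol and SAP*

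**What the plan says.** Three places give the intended exposure for the semen endpoint in terms of tablets.

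- Summary, burden and risks paragraph: "we want to measure improvement of semen parameters after at least 3 months use of study medication".
- Secondary Objectives: the change is "between baseline and 3 months intervention, based on pre-wash total motile sperm count (TMSC".
- Section 5.3, Semen analysis, opens the same way but adds a bracket: "once more after approximately 3 months of using study medication (ie. after three months of IUI treatment or IVF/ICSI". A few lines later it says that "the TMSC (evaluated at the start of treatment and after 3 months) will be analyzed" by change of treatment category. For IVF/ICSI the measurement "will be performed on the semen produced for IVF/ICSI as part of routine measurement before procedure".

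Section 5.3 gives no visit window and no minimum number of days from the first tablet.

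On entry, the Summary allows couples whose fertility treatment is already under way and lets couples start treatment directly. Section 1.2 admits "couples starting with 1st/ 2nd/3rd cycle of IUI (with/without ovarian stimulation", and the same range of cycles for IVF/ICSI.

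On biology, section 1.3 takes complete replacement of sperm to need 72 days: "In these first months the effect of the intervention is expected to be suboptimal due to the duration of the spermatogenesis (72 days before whole". For pregnancy the plan acts on this. It lowers the assumed gain from 7.3 to 6.5 points (section 1.3) and defines a secondary endpoint restricted to conceptions in months 4 to 6 (section 5.1.2).

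Section 5.1.2 also lists "Improvement between Impryl® and control group in fertilization rate and embryo-utilization rate in IVF/ICSI group". Sections 5.1.2, 5.3 and 7 attach no exposure condition to these two rates and do not say which cycle counts. Section 7 analyses them like the primary outcome and does not list them among the per-protocol outcomes.

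**The concern.** A site that follows the bracket in section 5.3 counts from the fertility treatment, whereas the endpoint it serves counts from the tablets. The two clocks agree only when both start together. An ejaculate collected before sperm renewal is complete contains sperm formed wholly or partly before the tablets could act. If such samples are mixed in, the differences in TMSC category, fertilization rate and embryo-utilization rate are pulled towards zero. A null result on these endpoints could then mean either no effect or too little exposure, and the planned analysis could not separate the two.

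The gap is notable because the protocol already uses the renewal argument elsewhere: for the pregnancy window, and in section 2.2 for a 72-day wash-out after other supplements. It does not use it for the endpoints measured most directly on sperm.

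**Working it through.** **Figures the plan states.** There is no power or effect figure for the semen, fertilization or embryo endpoints. The primary design does reproduce: 600 per arm, 20% versus 26.5%, two-sided 5% gives 76.0% power (pooled variance, no continuity correction), as section 1.3 states. This point changes nothing there.

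**Men concerned.** With 1200 men in the ratio 1:3:2 (section 1.3), IUI has 1200 × 3/6 = 600 and IVF/ICSI has 1200 × 2/6 = 400. The EM group has no follow-up semen analysis.

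**The two clocks.** Taking 30.44 days per month, 72 days is 72/30.44 = 2.4 months, and three months is about 91 days. A sample at a true three months of tablets clears the renewal time. What the wording permits is this:

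| Situation | Tablet exposure at the sample |
|---|---|
| Tablets and treatment start together, sample at 3 months | about 91 days |
| Treatment starts after the tablets, 3 months counted from treatment | more than 91 days |
| Treatment began before the tablets, 3 months counted from treatment | less than 91 days, possibly under 72 |
| IVF/ICSI procedure soon after randomisation | days to the procedure, possibly under 72 |

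For IVF/ICSI an early sample may not be followed by a later one, since section 2.2 describes the fertility intervention as six IUI cycles or one IVF/ICSI cycle. Fertilization and embryo-utilization rates come from the same procedure, so the last row applies to them without any rule pulling the other way.

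**Size, as illustration only.** Let f be the fraction of samples or cycles before day 72. Assume no effect before day 72, the full effect D after it, and the same f in both arms. Then

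average effect = (1 − f) × D.

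For a comparison with 80% power at the full effect (two-sided 5%, normal approximation, unchanged variance),

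power = Φ[(1 − f)(1.960 + 0.842) − 1.960], and the required sample size is multiplied by 1/(1 − f)².

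| f | Effect remaining | Power | Sample-size factor |
|---|---|---|---|
| 10% | 90% | 71% | 1.23 |
| 25% | 75% | 56% | 1.78 |
| 50% | 50% | 29% | 4.0 |

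The documents do not give f. The only allowance they make for early exposure is for the primary outcome: 6.5/7.3 = 89% of the full effect kept. That figure averages over six months of conception by all routes and does not carry over directly to endpoints tied to one ejaculate.

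**The case against.** The strongest reply is that the plan does name tablet use. Section 5.3 gives about three months of study medication first, the Summary and Secondary Objectives agree, and treatment appears only in a bracket. A reader might infer that the sample is timed by fertility treatment in place of tablet use. The documents do not support that: the sentence states both clocks and wrongly equates them.

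A reader might also infer that a couple entering at the third IUI cycle would be sampled after about 30 days of tablets. That requires cycles completed before randomisation to count towards the three months, and cycles to be monthly. Neither is stated, and one time-to-pregnancy definition in section 5.1.2 starts from treatment during the study, which points the other way.

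A third tempting step is to derive a large dilution by spreading retrievals evenly over three or six months. The documents give no retrieval timing, and section 1.3 expects a suboptimal early effect, not a zero one.

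It can further be said that immediate start is deliberate, that routine samples spare couples extra visits, and that an all-cycle comparison by randomised arm answers the same question as the primary outcome. This stands. It is a reason to keep the all-cycle comparison as the main analysis. It does not settle the conflict between the bracket and the endpoint definition, nor does it help a reader interpret a null result.

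**Conclusion.** The point holds in limited form. Section 5.3 equates two clocks that can differ, refers to TMSC at the start of treatment, and sets no window from the first tablet, so the exposure intended in the Summary and Secondary Objectives is not secured. Some samples can precede 72 days of tablet use. The fertilization and embryo-utilization rates have no exposure condition and no exposure analysis, although the plan makes that allowance for pregnancy.

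The harm is confined to secondary endpoints. The timing rules apply alike to both randomised arms, so the expected result is dilution towards no difference and not a spurious effect. Its size is unknown. The values of 90%, 75% and 50% remaining rest entirely on assumed fractions of early samples and on no effect before day 72; a partial early effect would make the loss smaller. This should be corrected because a stated timing rule conflicts with the endpoint it serves, but it does not threaten the primary analysis.

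**What to change.** 1. **Semen sample.** Reconcile the Summary, Secondary Objectives and section 5.3. Delete the bracket, and define the follow-up TMSC as the first routine pre-wash TMSC at or after three months from the first tablet, while tablets are still being taken. Report earlier samples separately. State which sample is the baseline in place of the loose reference to the start of treatment.
2. **Data fields.** Record the dates of first tablet, semen sample and oocyte retrieval. At present section 5.2 logs the date of issue, and section 5.3 collects consumption and the date of a positive test; the other dates are not listed as study data.
3. **Fertilization and embryo-utilization rates.** Keep the all-cycle randomised comparison as the main analysis. Add a pre-specified supportive analysis of each couple's first study retrieval by days of tablet use (under 72 versus 72 or more), with an arm-by-exposure term.

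The cost is protocol and SAP wording and a few data fields, with no extra visits. Fewer men and cycles qualify, so intervals widen. Couples whose only IVF/ICSI cycle is early contribute neither a qualifying TMSC nor anything to the exposed estimate. Couples who conceive early also drop out of that estimate. If the supplement affects early conception, the remaining arms are no longer fully comparable, so the exposed estimate must be labelled supportive and read beside the all-cycle result.

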SUMMARY

Rationale: Infertility is a worldwide problem and about 10%-15% of all couples will be affected by the inability to have children. In approximately 50% of infertile couples a male factor is involved. In the past decade, the role of oxidative stress on sperm has been researched thoroughly and found to be the problem in 30% to 80% of male infertility cases. Impryl® is a nutritional supplement which works on the metabolic system and regulation of oxidative stress by activating the 1-Carbon cycle and therefore recycling of homocysteine.

Objective: To determine the effectiveness of nutritional supplement Impryl® in men of infertile couples on ongoing pregnancy rate, with or without assisted reproduction technology (ART).

Study design: Multicentre, randomised double blind placebo controlled clinical trial/superiority study.

Study population: All participants in this study are male adults, age 18-50 years, part of a couple that is diagnosed with infertility, regardless the outcome of semen analysis. The couple will either start or is already started with fertility treatment, i.e. expectative management (EM, duration 6 months), intra-uterine insemination (IUI) with or without ovarian stimulation (mild ovarian hyperstimulation (MOH) or ovulation induction (OI)), either in vitro fertilization (IVF) or intracytoplasmic sperm injection (ICSI) treatment.

Intervention: Impryl® or placebo, with identical appearance one tablet each day for a total duration of maximal 6 months. Patients can start directly with fertility treatment and/or to conceive.

Main study parameters/endpoints: The primary outcome is the number of ongoing pregnancies confirmed by ultrasound at ≥ 10 -12 weeks, and conceived in the time window between randomization up to and including month 6 of intervention use. Secondary outcomes are change in semen parameters between baseline and 3 months intervention in IUI/IVF/ICSI group, based on (pre-wash) total motile sperm count (TMSC), leading to a different fertility treatment categorisation. Furthermore the number of pregnancies conceived in the optimal intervention time window, the overall number of pregnancies, time to pregnancy, embryo fertilization rate in IVF/ICSI, embryo-utilization rate in IVF/ICSI, number of miscarriages and live birth rate are documented within the study period of 15 months. The occurrence of adverse events will be reported.

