2.1 Investigational product/intervention

Impryl® tablets will be produced by Labomar SRL who will also produce an identical looking placebo tablet. Patients start directly with study medication for a total duration of maximum 6 months.

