5.3 Study procedures

Couples matching the inclusion criteria will be asked to participate in the trial. If after diagnostic work up the diagnosis infertility for the couple remains, both are asked for informed consent. After signing informed consent, the male patient will be randomised and allocated to Impryl® or placebo (double blinded).

Medication

Patients can directly start using the food supplement or placebo. Impryl® or placebo will be taken for a total duration of 6 months and will be directly stopped after having a positive pregnancy test.

Baseline characteristics

Patients are asked to report on these characteristics by a short questionnaire. Patients will receive an automatic email invitation directly after randomisation and are asked to provide this information online in the Castor database system

Lifestyle and outcome characteristics

Patients will be asked once every month to report on occurrence of pregnancy (with date of positive test), changes in weight and diet, changes in habit of smoking and drug or alcohol use, occurrence of fever and change in activities increasing scrotal temperature (hot baths, sauna, race cycling). Furthermore patients are instructed about taking note of the total amount of consumed study medication (used boxes and tablets). There is a question about the occurrence of adverse events. Patients will receive an automatic email and are asked to provide this information online in the Castor database system. When a pregnancy has been reached during the 6 months use of study medication the monthly questionnaires will be stopped, because there is no more necessity to record on lifestyle changes and treatment compliance.

Semen analysis

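### The semen outcome has two different first samples, and one of them can be taken after the first tablet, which can attenuate the estimated effect

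*Combined protocol and SAP*

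**What the plan says.** The change in semen quality is a secondary outcome. It is scored as a shift in treatment category based on pre-wash TMSC, and covers only Radboudumc and the sites that measure pre-wash TMSC routinely (Section 5.1.2). The documents describe its first value in three ways:

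- Section 5.3, opening of the semen paragraph: "Semen analysis will be performed two times: once during diagnostic work-up". This is the standard-care analysis by WHO criteria. The second analysis comes "once more after approximately 3 months of using study medication (ie. after three months of IUI treatment or IVF/ICSI").
- Section 5.3, later in the same paragraph: "the TMSC (evaluated at the start of treatment and after 3 months) will be analyzed according to changes in allocated treatment category".
- Objectives: "between baseline and 3 months intervention, based on pre-wash total motile sperm count (TMSC"), with baseline not defined further.

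On the timing of tablets, Section 2.1 says "Patients start directly with study medication for a total duration of maximum 6 months", and Section 5.3 says "Patients can directly start using the food supplement or placebo". On the timing of fertility treatment, the Summary says "The couple will either start or is already started with fertility treatment", and Section 1.2 admits couples at a first, second or third cycle of IUI or IVF/ICSI.

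Section 7 codes the category change and analyses it with a fixed effects linear model adjusted for centre and stratum. It does not say from which sample the change is counted.

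**The concern.** A change score needs one baseline, and in a randomised comparison that baseline should precede exposure to the study product. Here one paragraph names two first samples that differ in date and method. The work-up sample precedes consent and randomisation and follows WHO criteria. A sample at the procedure does not fully follow those criteria, as Section 5.3 itself says, and no rule places it before the first tablet.

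If the later wording is followed, some men on Impryl could have part of their response already in the baseline, and the measured change would understate it. The placebo arm has no such response to lose, so the difference between arms shrinks. This outcome is the trial's direct measure of an effect on sperm, and a null result would be hard to read: it could mean no effect, or a baseline taken too late. Leaving the baseline undefined also leaves the choice open until the analysis.

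**Working it through.** **The plan's own figures.** No effect size, standard deviation or power is given for the semen outcome, so there is no figure to reproduce for it. The only design calculation concerns the primary outcome (Section 1.3: 20% against 26.5%, 600 per arm, two-sided 5%). With the pooled-variance formula: mean rate 0.2325; SE under the null = √(2 × 0.2325 × 0.7675 / 600) = 0.02439; SE under the alternative = √((0.20 × 0.80 + 0.265 × 0.735) / 600) = 0.02432; (0.065 − 1.96 × 0.02439) / 0.02432 = 0.71, which gives 76% power. The stated figure reproduces, and nothing in this point touches it.

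**Which treatment is meant.** The possible readings of the later Section 5.3 wording are:

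1. *The fertility procedure.* The sentence that leads into it speaks of semen analysed at the time of treatment, meaning the insemination or IVF/ICSI sample, and pre-wash TMSC is measured when semen is used for a procedure. This is the most natural reading.
2. *The study tablets.* No semen sample is scheduled when tablets start.
3. *Loose wording for the work-up value* that set the allocated category. This agrees with two analyses in total, but the words do not say it.

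Each reading needs a correction to the text.

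**Where the sample falls under reading 1.** Tablets may start directly after randomisation.

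- Couple starting fertility treatment after randomisation: the first procedure sample can follow the first tablet.
- Couple already in treatment at entry: the start of treatment can precede randomisation, and nothing is lost.
- Couple with one IVF/ICSI cycle (the course described in Section 2.2): there may be only one procedure sample, hence no separate baseline.

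Pre-tablet and post-tablet baselines could therefore occur within the same stratum, and the model has no term to separate them. Section 5.3 also treats 3 months of tablets and three months of IUI or IVF/ICSI as the same, although the two can start on different dates.

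**Illustrative size.** The documents give no interval from first tablet to first procedure sample, so the day is an assumption. Section 1.3 gives 72 days for whole renewal of sperm and expects a suboptimal effect in the first months. Assume the full effect is present by day 72 and at follow-up (about day 90). The share lost equals the share already present at the baseline sample on day t: t/72 for linear build-up, (t/72)² for late build-up, and 0 if nothing appears before day 72.

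| Baseline sample, days after first tablet | Linear | Late (quadratic) | Nothing before day 72 |
|---|---|---|---|
| 7 | 10% | 1% | 0% |
| 14 | 19% | 4% | 0% |
| 28 | 39% | 15% | 0% |
| 30 | 42% | 17% | 0% |
| 42 | 58% | 34% | 0% |

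These are losses in the affected men only. If half the men had a day-28 baseline and the rest a pre-tablet one, the average loss under the linear curve would be 0.5 × 39% = 19%. The shares describe a continuous effect. The outcome is a category-shift score, so they do not carry over one for one.

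**The case against.** The strongest reply is that Section 5.3 says semen is analysed twice. If only two analyses exist, the start-of-treatment value may simply be the work-up value, and the Objectives, which speak of baseline and 3 months, fit that. The word treatment also refers to the study product elsewhere (the title of Section 2, the treatment arms in Section 7). This stands as a reason not to treat the harmful reading as certain. It does not remove the need to choose, because the text as written supports either sample.

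A reader might infer that part of any effect will be subtracted out. The documents do not support that. Three things must hold together: treatment means the fertility procedure, the tablets began before that sample, and some effect on semen was present by then.

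A reader might also infer that all IVF/ICSI couples, 2/6 × 1200 = 400, would be scored as no change. That is not supported either. No text says one sample serves as both baseline and follow-up; a missing sample would be missing, not zero. The outcome covers only a subpopulation, and some couples have more than one cycle.

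Nor would the result be uninterpretable. Randomisation is stratified by fertility treatment and centre, and the model adjusts for both, so differences in baseline practice between sites and strata fall equally on the two arms.

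**Conclusion.** The inconsistency is real and unresolved: one secondary outcome has two first samples, and under the more natural reading one of them can follow the first tablet. That can bias the estimated effect towards no difference. The amount cannot be calculated from the documents. Under the stated assumptions it runs from 0% (no effect before day 72) to about 40% in men with a day-30 baseline and linear build-up, and an earlier sample or later onset gives less. The day and the curve are assumptions, and the percentages are a guide only for a category score.

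Both arms follow the same schedule, so with no true effect the comparison stays balanced and type I error is not inflated. The primary outcome and the sample size are unaffected. The point deserves correction because the remedy is cheap and the outcome bears directly on the proposed mechanism.

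**What to change.** In Section 5.3 and Section 7:

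- Define the baseline for every couple in this analysis as the TMSC from the diagnostic work-up, taken before randomisation.
- Strike the words that place the first TMSC at the start of treatment.
- Count the 3 months to the follow-up sample from the first tablet, and record the dates of the first tablet and of each sample.
- Add baseline TMSC category as a covariate to the fixed effects linear model, beside centre and stratum. A man already in the highest category cannot improve, so the possible shift depends on where he starts, and adjustment should improve precision.

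The cost is wording and a few dates in the database; the work-up sample is already standard care. The downside is that this sample may be old, above all in couples entering at a second or third cycle, and it is measured by a different method from the follow-up sample. Both apply equally to the two arms, so they may add noise but do not favour either arm.
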